**NCT Number: NCT04373421**

**Study Protocol, and Statistical Analysis Plan**

**Study Protocol**

This randomized double-blind clinical trial will be conducted in Ankara Yıldırım Beyazıt University Oral and Maxillofacial Surgery Clinic and Van Yüzüncü Yıl University. Ethical approval of the study was obtained from Van Yüzüncü Yıl University Faculty of Medicine Clinical Research Ethics Committee in accordance with the Declaration of Helsinki (Decision Date and Number: 01.08.2018-08). Signed informed consent will be obtained from all patients.

90 healthy individuals who need third molar surgery will be included in this study. Inclusion criteria: Between 18-40 years of age, having asymptomatic unilateral mandibular impacted third molars (mesioangular) with similar angular positions according to the Winter classification and a similar degree of impaction according to Pell and Gregory's classification (class II, level B). Patients with a history of smoking, drug use, and pericoronitis associated with the lower third molar will be excluded. Pregnant and lactating women, patients with periodontal problems in the adjacent second molars (ie, increased periodontal depth, gingival recession), or patients without adjacent second molars on the operative side will also be excluded.

The predictive variable will be the type of mouthwash used in the study (St. John's wort oil and olive oil) and the control (chlorhexidine gluconate + benzylamine hydrochloride) groups. The outcome variable will be patient-reported pain and difficulty in jaw function, trismus, facial swelling, the number of analgesics used in the first postoperative week, and postoperative periodontal status.

All patients included will be randomly divided into 3 groups. St. John's wort oil will be given; Extra virgin olive oil will be given to the patients in the second group, and the mouthwash containing chlorhexidine gluconate and benzylamine hydrochloride will be given to the patients in the third group. Randomization will be performed by permutation method in MedCalc 11.5.1 software (MedCalc Software Inc, Ostend, Belgium). Three types of mouthwash will be given to the clinicians without notifying the surgical procedure or

postoperative controls, which are individually placed in boxes by the assistant personnel categorized as group 1, group 2 and group 3.

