A 7-day planned pain diary will be given to patients to evaluate postoperative pain and jaw function. To record the level of pain, patients will be instructed to grade on 100 mm visual analog scales (VAS) where 0 indicates no pain and 100 indicates the worst pain imaginable. To assess the difficulty in jaw function, patients will be asked to rate it at 100 mm VAS, where 0 indicates no limitation and 100 indicates severe limitation. They will also be asked to note how many painkillers they take per day. Patients will be evaluated for facial

swelling and trismus on postoperative 1st, 3rd and 7th days. In addition, complications such as alveolitis and infection will be recorded observationally.

All clinical periodontal assessments were to be measured by a blind examiner and mesio-buccal, mid-buccal, disto-buccal and disto-lingual were selected around adjacent second molar measurements for four regions. The plaque index defined by Silness and Loe will be used to evaluate patients' dental plaque status. Plaque thickness on the third gum of the teeth will be evaluated. The scores for each unit will then be summed up and divided by the total number of areas evaluated to arrive at the plaque index. The gingival bleeding index, introduced by Ainamo and Bay, will be used in the assessment of patients' gingivitis. The second molar will be probed gently with a periodontal probe (Williams probe, Hu-Friedy, Chicago, IL, USA) and then if bleeding occurs within 10 seconds, the bleeding sites will be noted as "positive". The number of positive bleeding zones will be divided by the total number of zones present and multiplied by 100 to express the gingival bleeding index as a percentage. Both the plaque index and the gingival bleeding index will be recorded preoperatively and on the 7th and 14th days and 1 month after surgery. The probing pocket depth will be measured by inserting a periodontal probe into the gingival groove until resistance is felt, and the measurements will be recorded to the nearest millimeter. Probing depths will be evaluated for the second molar tooth before surgery and 1 month after surgery. If there is gingival recession in the second molars, the distance between the cement-enamel junction and the free gingival border will be measured at the last follow-up visit.

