### **Statistical Analysis Plan**

Based on previous trial studies, a power analysis was performed using the Power Analysis of Sample Size (PASS) software program, showing that the Standard deviation ( $\sigma$ ) for pain ranged from 4.87 to 5.07. For this reason, the standard deviation was accepted as 5. The effect size was accepted as (d) 2 by the researcher for the 95% confidence coefficient and approximately 80% power value, and the Z value was used as 1.96 for 0.05. type I error rate. Using the sample size calculation equation, the sample size was found to be 24 ( $n = Z^2\sigma^2 / d^2$ ). Descriptive statistics (frequency, mean and standard deviation) were determined for each variable. Kruskal-Wallis H test will be used for comparisons between groups, and Wilcoxon signed rank test will be used for in-group comparisons. All analyzes will be performed using SPSS Version 21.0 (SPSS, Inc., Chicago, IL). A value of  $p < 0.05$  will be considered statistically significant for all analyzes.

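### No primary outcome, no multiplicity rule, and no planned test or interval comparing either oil with the control rinse

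*Combined protocol and SAP*

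**What the plan says.** The Study Protocol section describes three randomised arms ("All patients included will be randomly divided into 3 groups"): St. John's wort oil, olive oil, and a chlorhexidine-benzylamine rinse that it labels as control ("the control (chlorhexidine gluconate + benzylamine hydrochloride) groups"). Outcomes appear in one unranked list: "The outcome variable will be patient-reported pain and difficulty in jaw function, trismus, facial swelling", followed by "the number of analgesics used in the first postoperative week, and postoperative periodontal status". On pain it adds "A 7-day planned pain diary will be given to patients to evaluate postoperative pain and jaw function". Swelling (five facial distances) and trismus are measured on days 1, 3 and 7. Plaque and bleeding indices are taken at three postoperative visits, and probing depth at one. Recession is measured at the last visit if present.

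The Statistical Analysis Plan section bases the sample size on a standard deviation that "for pain ranged from 4.87 to 5.07". Its inferential content is then "Kruskal-Wallis H test will be used for comparisons between groups, and Wilcoxon signed rank test will be used for in-group comparisons", and a p-value below 0.05 "will be considered statistically significant for all analyzes". The only other output is frequencies, means and standard deviations. It gives no primary outcome, pairwise procedure, multiplicity rule, or estimate or interval for a difference between arms.

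**The concern.** A three-arm trial with a named control exists to say whether either new rinse differs from that control. The Kruskal-Wallis test addresses only whether all three arms share one distribution. A significant result may come from the two oils differing from each other, and it gives neither the direction nor the size of any difference from control. The signed-rank tests compare no arms. A change within one arm mixes ordinary healing with any effect of the rinse.

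Because no outcome is ranked and one threshold covers everything, any of many p-values could become the headline result. Sizing the trial on pain does not prevent this: with seven diary days and no stated summary, the pain analysis itself can be chosen after the data are seen.

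**Working it through.** **1. The plan's own figure.** n = Z²σ²/d² = 1.96² × 5² / 2² = 24.01, which matches the stated 24. Pain is therefore the sizing variable. The calculation does not say which day or summary of pain has an SD of 5.

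**2. How many between-group tests?** The plan does not list them, so the count is a range:

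| Reading | Count |
|---|---|
| One test per listed outcome | 6 |
| Periodontal status split into plaque, bleeding, probing depth, recession | 5 + 4 = 9 |
| By day or visit: pain 7, jaw function 7, analgesics 1, trismus 3, swelling 3, plaque 3, bleeding 3, probing depth 1, recession 1 | 29 |
| As above, five facial distances separately (15 swelling tests instead of 3) | 29 + 12 = 41 |

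Without a recession test, the last three counts become 8, 28 and 40. In-group tests are not counted.

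**3. Chance of at least one false positive.** If tests are independent it is 1 − 0.95^k. The correlated column comes from simulated null Kruskal-Wallis tests with 30 per arm (90/3, equal allocation assumed). The within/between-outcome correlations, 0.5/0.2 to 0.8/0.5, are assumptions with no source in the documents.

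| k | Independent | Correlated |
|---|---|---|
| 6 | 26% | 21-25% |
| 9 | 37% | 28-35% |
| 29 | 77% | 45-67% |
| 41 | 88% | 51-75% |
| Pain only, 7 days | 30% | 16-24% |

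Without recession, the independent figures are 34% (k=8), 76% (k=28) and 87% (k=40).

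**4. What a significant omnibus test leaves open.** This was simulated with normal data, 30 per arm and 40,000 runs. The last column is the share of significant Kruskal-Wallis results in which neither oil differs from control by Mann-Whitney at 0.05. The plan's 2/5 gives 0.4 SD.

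| Shift in SD (control, oil 1, oil 2) | Kruskal-Wallis significant | Neither oil differs from control |
|---|---|---|
| 0, 0.4, 0.4 | 31.2% | 0.9% |
| 0, 0.4, 0.2 | 24.5% | 5.1% |
| 0, 0.4, 0 | 30.9% | 18.8% |
| 0, 0.4, −0.4 | 75.9% | 26.2% |

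**5. Does a gated pairwise procedure control error?** With three arms, if any two pairwise null hypotheses hold, all three arms are equal. Kruskal-Wallis at 0.05 followed by pairwise tests at 0.05 is therefore a closed procedure. In simulation with all arms equal, any pairwise rejection occurred in 4.9% of trials gated and 11.8% ungated. With one arm shifted by 5 SD, the remaining true-null pair was rejected in 4.5-4.8%.

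**6. Power.** If d = 2 and SD = 5 apply to the chosen pain summary, simulated Mann-Whitney power for one oil-control contrast with 30 per arm is about 31% ungated and 23% after the gate (other oil equal to control).

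**The case against.** The strongest reply is that the Study Protocol makes type of mouthwash the explanatory variable and states no oil-versus-control hypothesis, so a three-group test answers the question as posed. Comparisons between groups could also be read to include pairwise follow-up. But the protocol does name a control, and no follow-up test is specified. Three unadjusted Mann-Whitney tests would give a false positive in about 12% of null trials.

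Second, the high error rates belong to test lists that the plan never states. That is fair. Only the count of six comes straight from the outcome list, and the upper end moves with counting choices: analgesics tested by day would add 6, giving 47 tests and 91% if independent. The correlated figures also depend on the assumed structure. Treating the four periodontal measures as one correlated block lowers the nine-test range to about 27-32%.

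Third, the omnibus-gap figures run from 1% to 26% over an unknown pattern of effects. They illustrate the gap and do not measure it, but the logical point stands without them.

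Fourth, pain is recognisably the lead outcome, and the data collected would allow every contrast. Both are true. Neither fixes the pain summary or the contrast before the data are seen.

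**Conclusion.** The concern holds. Followed as written, the plan produces no test or interval for either oil against control, names no primary outcome, and does not control error across outcomes. This follows from the text and needs no assumption.

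The size of the error problem is conditional. It is moderate, 21-26%, with one test per listed outcome. It is high, 45-88%, only if outcomes are split by day, visit or distance. A single prespecified pain test would sit at 5%, but the plan does not specify one. The ranges rest on equal allocation, the assumed correlations and the counting choices shown above. The plan should be amended before analysis.

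**What to change.** Amend the Statistical Analysis Plan as follows.

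1. Designate pain VAS as the single primary outcome. Give it one prespecified summary, for example each patient's mean over the seven diary days, and a rule for missing days. Test it by Kruskal-Wallis at 0.05.
2. If that is significant, compare each oil with control, and oil with oil, by Mann-Whitney at 0.05, with no further adjustment. Report Hodges-Lehmann differences with 95% intervals in any case. State that intervals after a non-significant Kruskal-Wallis test are descriptive: in simulation, at least one unadjusted pairwise result fell below 0.05 after a non-significant gate in 6.9% of trials with no true difference.
3. Label all other outcomes secondary and exploratory, with one stated summary each, and say whether swelling is one combined measure or five. Give both oil-control differences with 95% intervals and make no confirmatory claim. With 8 secondary outcomes, 8 × 2 = 16 intervals, of which 0.05 × 16 = 0.8 would exclude zero by chance. With five distances there are 12 outcomes, 24 intervals and 1.2. Recession is best given as the share of patients with it. The protocol measures it as a distance, so the SAP should state this change.
4. Treat in-group signed-rank tests as descriptive, and do not read p>0.05 as equivalence.

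Two direct oil-control contrasts at 0.025 would be an acceptable alternative to the gate, with similar power (about 21-22% per contrast).

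The cost is a few SAP sentences and minor extra analysis, with no new data. Fewer results can be called significant. Power for an oil-control contrast is low (about 23% gated), and the SAP should state this.

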All procedures will be performed by the same surgeons in each center, using a standard protocol in each medical center. Local anesthesia will be administered using 0.01 mg / ml epinephrine and 2 ml articaine hydrochloride 40 mg / ml (Maxicaine Fort, VEM Drug, Istanbul, Turkey). Horizontal incision no. 15 scalpel blades and full thickness mucoperiosteal flaps will be removed. In all surgical procedures, bone removal and / or tooth cutting will be performed under copious irrigation. Following extraction, the granulation tissues will be removed and the post-extraction cavity washed with sterile 0.9% saline solution. After the bleeding is controlled, the mucoperiosteal flap will be repositioned with a 3.0 silk suture. Paracetamol (Parol® 500 mg, Atabay Kimya Sanayi, Istanbul, Turkey) was prescribed to the patients to use when necessary, with a maximum of 4 doses per day after surgery. Patients will be instructed to maintain a gentle diet for the first 24 hours and to avoid mouthwashing, brushing, and flossing. In addition, they will be asked to rinse their mouths with 15 ml of mouthwash 3 times a day for 30 seconds and continue until the 7th day after surgery.

The maximum mouth opening (MMO) will be measured in millimeters with a caliper from the incisal edge of the right upper and lower incisors. To evaluate the trismus, the percentage difference in MMO at the postoperative period (B), subtract the preoperative measurement (A) from the postoperative measurement, and then divide the preoperative measurement (A) and multiply by 100 (percentage difference =  $[B - A] / B \times 100$ ) . Facial swelling will be assessed using a thread and a millimeter ruler and five additional measurements will be made: distance I (from mandible to labial commissure); distance II (from angle of mandible to nose border) distance III (from the angle of the mandible to the outer corner of the eye); distance IV (from angle of mandible to tragus) and distance V (from mandible to soft pogonion). To evaluate the changes in the above distances in the postoperative period, the percentage of facial swelling will be calculated by subtracting the preoperative measurement from the postoperative measurement and then dividing it by the preoperative measurement and multiplying by 100.

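### The preoperative plaque, bleeding and probing values have no stated role in comparing the rinses, which gives up precision if those values are prognostic

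*Combined protocol and SAP*

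**What the plan says.** The Statistical Analysis Plan section gives two tests. Between groups, "Kruskal-Wallis H test will be used for comparisons between groups". Within groups, "Wilcoxon signed rank test will be used for in-group comparisons". It names no covariate, stratum or change score, and does not mention centre.

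The Study Protocol section collects a baseline for all three periodontal measures. Plaque and bleeding indices "will be recorded preoperatively and on the 7th and 14th days and 1 month after surgery". For the third, "Probing depths will be evaluated for the second molar tooth before surgery and 1 month after surgery". Trismus and facial swelling are defined as percentage differences that use the preoperative measurement. (For trismus, the words and the formula divide by different measurements. That is a separate matter, and the preoperative value enters either way.) Plaque, bleeding and probing have no such definition.

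The trial has two centres: "All procedures will be performed by the same surgeons in each center, using a standard protocol in each medical center". On allocation, "Randomization will be performed by permutation method in MedCalc 11.5.1 software"; the text does not say whether there was one list or one per centre. Eligibility excludes "patients with periodontal problems in the adjacent second molars (ie, increased periodontal depth, gingival recession", which limits how much the periodontal baseline can vary.

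**The concern.** Kruskal-Wallis compares one number per patient across groups. For the periodontal outcomes the plan does not say whether that number is the postoperative value or the change from baseline. If it is the postoperative value, the preoperative measurement plays no part in comparing the rinses. If it is change, the baseline enters with a fixed weight that suits only high correlations. The within-group Wilcoxon test can use the baseline, but it does not compare rinses.

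What is at stake is power, in a trial with about 30 patients per arm. Centre is a smaller form of the same issue: each site has its own surgeons, so any surgeon effect falls along centre lines, and the analysis has no centre term.

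**Working it through.** **1. The plan's own figure.** n = Z²σ²/d² = 1.96² × 5² / 2² = 3.8416 × 25 / 4 = 24.01, so the stated 24 reproduces. It concerns pain and contains no correlation, so the periodontal point does not depend on it. Only the ratio 2/5 = 0.4 SD is used below, in step 6.

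**2. Inputs.** From the documents: 90 patients, three groups, two centres, significance level 0.05, Kruskal-Wallis between groups. Assumed, because the documents do not give them: equal arms of 30, centres of 45 and 45, normal errors, the baseline-outcome correlation r, a shift in one arm only, and the centre effect.

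**3. Algebra.** Take the variance of the unadjusted postoperative value as 1. Change from baseline has variance 2 − 2r; linear adjustment for baseline leaves 1 − r².
- At r = 0.2, 0.3, 0.5, 0.7, change gives 1.60, 1.40, 1.00, 0.60.
- At the same r, adjustment gives 0.96, 0.91, 0.75, 0.51.
- Change beats the postoperative value only when r exceeds 0.5. Adjustment is never worse than change, because (2 − 2r) − (1 − r²) = (1 − r)², which cannot be negative.
- Adjusting 30 per arm is like having 30/0.91 = 33, 30/0.75 = 40 or 30/0.51 = 59 per arm at r = 0.3, 0.5, 0.7.

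**4. Simulated power.** One arm shifted 0.6 SD, no centre effect, 20,000 runs. Rank ANCOVA is a linear model on ranks with group, centre and ranked baseline, so its figures already pay for an unneeded centre term.

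| r | Kruskal-Wallis, postoperative | Kruskal-Wallis, change | Rank ANCOVA | Gain over postoperative | Gain over change |
|---|---|---|---|---|---|
| 0.2 | 0.623 | 0.425 | 0.635 | 0.012 | 0.210 |
| 0.3 | 0.628 | 0.476 | 0.661 | 0.033 | 0.185 |
| 0.5 | 0.624 | 0.624 | 0.738 | 0.114 | 0.114 |
| 0.7 | 0.624 | 0.852 | 0.884 | 0.260 | 0.032 |

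Type I error was 0.048 to 0.052 for all three methods. With a centre explaining 5% of variance and ignored, Kruskal-Wallis gave 0.049 in 20,000 runs. A shorter run of 4,000 had shown 0.062, but the group labels are exchangeable under unstratified randomisation, so the longer run is the one to rely on.

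**5. Narrowed baseline.** Same shift, 10,000 runs, with the upper 20% or 50% of baseline values removed to imitate the eligibility limits.
- r = 0.3 falls to 0.23 or 0.19. Postoperative 0.622 or 0.629, change 0.520 or 0.568, rank ANCOVA 0.631 or 0.635. The gain over the postoperative value is about 1 point.
- r = 0.5 falls to 0.40 or 0.33. Postoperative 0.628 or 0.629, change 0.632 or 0.634, rank ANCOVA 0.698 or 0.669. The gain is 7 or 4 points.
- r = 0.7 falls to 0.60 or 0.51. Postoperative 0.624 or 0.630, change 0.791 or 0.738, rank ANCOVA 0.806 or 0.744. The gain is 18 or 11 points over the postoperative value, but under 2 over change.

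**6. Centre, for pain.** Shift 0.4 SD, 40,000 runs, centre effects of 0, 0.2, 0.3, 0.5 and 0.8 SD.
- Allocation not by centre: Kruskal-Wallis 0.315, 0.312, 0.307, 0.297, 0.274; rank model with centre 0.316, 0.316, 0.315, 0.315, 0.310. Gains are 0.1, 0.4, 0.8, 1.8 and 3.6 points.
- The centre-stratified rank test, in the same setting, gave 0.307, 0.308, 0.307, 0.306, 0.306. It is below Kruskal-Wallis at 0 and 0.2 SD.
- Allocation by centre: plain Kruskal-Wallis has type I error 0.048, 0.048, 0.047, 0.042, 0.030 and power 0.312, 0.308, 0.302, 0.285, 0.245. The rank model with centre has power 0.317 to 0.318 throughout.

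**The case against.** The strongest reply is that an unadjusted rank test in a randomised trial is valid, so this is a preference about efficiency. That stands as to validity. A reader might infer that leaving out baseline or centre biases the comparison or inflates type I error. The documents do not support that, and the simulated error rates contradict it.

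Second, the loss is conditional. A reader might infer that precision is certainly lost. It is lost only if the baseline or centre is prognostic, and the documents give no correlation and no centre variance. In a separate 4,000-run check with r = 0 and no centre effect, adjustment gained nothing (0.63 in both). This objection stands.

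Third, the large gains are best cases. Eligibility narrows the baseline, and the scales are coarse: for probing depth, "the measurements will be recorded to the nearest millimeter", and a bleeding index from four sites takes only five values. A 4,000-run simulation used five levels, 70% or 85% of baselines at zero, and 30% of unshifted postoperative values at zero. At latent r of 0.3 and 0.5, rank ANCOVA gave 0.63 and 0.66 (70%) or 0.61 and 0.64 (85%). The postoperative value gave 0.61 and 0.60, or 0.60 and 0.60; change gave 0.56 and 0.63, or 0.58 and 0.63. The gain is then 1 to 6 points over the postoperative value, and on these rounded figures 1 to 3 over whichever Kruskal-Wallis choice happens to be better. At latent r = 0.7 the gain over the postoperative value was still 10 to 14 points. This objection limits the size of the point but does not remove it: the plan does not commit to either variable, and the better one depends on an unknown r.

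Fourth, centre. A reader might infer that ignoring centre is a serious weakness, or that allocation was not by centre. Neither follows. For pain the gain is under 1 point up to 0.3 SD, and the text is silent on how the list was made.

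**Conclusion.** The point holds for plaque index, bleeding index and probing depth. A collected baseline has no stated role in the only test that compares rinses, and the test gives up precision to the extent that the baseline is prognostic. With 30 per arm and a 0.6 SD shift in one arm, both assumed, the gain from rank ANCOVA runs from about 1 to 26 points over the postoperative value as r goes from 0.2 to 0.7, and from about 21 down to 3 points over change. With a baseline narrowed by eligibility, 1 to 7 points over the postoperative value is the more cautious expectation at unrestricted r of 0.3 to 0.5. Rank ANCOVA was at least as powerful as both alternatives in every case tried, so the choice does not require knowing r.

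This is an inexpensive improvement to a valid plan. The centre term is secondary. It matters more if the list was made per centre, because plain Kruskal-Wallis is then conservative.

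**What to change.** For plaque index, bleeding index and probing depth, replace plain Kruskal-Wallis with one prespecified analysis at each postoperative visit (day 7, day 14 and 1 month for the two indices; 1 month for probing depth). That analysis is a rank ANCOVA of the postoperative value: a general linear model on ranks, with rinse group, ranked preoperative value and centre as terms. Do not include a switch to another test that depends on the observed distribution, since that would reopen the choice.

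Optional, for the other outcomes: keep each outcome as defined and use a rank model with rinse group and centre. Avoid the centre-stratified rank test, which can lose power when centre effects are small. State whether the permutation list was made per centre.

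The cost is SAP wording and one degree of freedom per added term: with 90 patients and three groups, error degrees of freedom go from 90 − 3 = 87 to 85 when baseline and centre are both added. Ranking followed by a general linear model runs in the SPSS already planned, and no new data are needed.

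### The within-arm Wilcoxon tests share the p < 0.05 rule with the randomised comparison, but their results cannot be attributed to a rinse

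*Combined protocol and SAP*

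**What the plan says.** The Statistical Analysis Plan names two tests. For the randomised question, "Kruskal-Wallis H test will be used for comparisons between groups". For change over time inside each arm, "Wilcoxon signed rank test will be used for in-group comparisons". One threshold covers both: a p-value under 0.05 "will be considered statistically significant for all analyzes". The plan does not list the outcomes or pairs of time points for the within-arm tests, does not give their purpose, and does not call them descriptive or secondary.

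The Study Protocol section makes the type of mouthwash the predictor. All three arms rinse until day 7, with St. John's wort oil, olive oil, or a chlorhexidine-benzylamine mouthwash as control. All patients have the same type of surgery and may take paracetamol as needed. They are told not to use mouthwash for the first 24 hours.

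Mouth opening and five facial distances are measured on days 1, 3 and 7 and expressed as change from the preoperative value. Plaque and bleeding indices are recorded before surgery, on days 7 and 14 and at 1 month. Probing depth is recorded before surgery and at 1 month. Pain, jaw function and analgesic use come from a 7-day postoperative diary, and no preoperative diary value is described.

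**The concern.** The null hypothesis of a signed rank test within one arm is that nothing changed between two readings. The stated predictor poses a different question: whether the outcome differs between rinses. Between any two readings in this trial come surgery, recovery and analgesic use, all common to the three arms. Rejecting the within-arm null shows that patients changed, not why.

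Day 1 is the plainest case. Swelling and mouth opening are measured then, yet rinsing is withheld for the first 24 hours, so the change from the preoperative value arises largely or wholly before any rinse is used.

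Two misreadings are at stake. If the shared change is large, every arm shows a significant change and every rinse may seem active. If it is moderate, some arms reach significance by chance and others do not, and that pattern may be taken as a difference between rinses. Either can happen when the rinses are identical. Because all tests share one threshold, nothing in the plan guards against this.

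**Working it through.** **The plan's own figure.** The only computed figure is the sample size. The inputs are "the Z value was used as 1.96 for 0.05", "the standard deviation was accepted as 5" and "The effect size was accepted as (d) 2 by the researcher". Then n = Z²σ²/d² = 1.96² × 5² / 2² = 3.8416 × 25 / 4 = 24.01, which reproduces the stated 24. The point does not depend on it.

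**Number of within-arm tests the schedule allows.** If each postoperative reading is compared with its preoperative value:
- mouth opening: 3
- facial distances: 5 × 3 = 15
- plaque index: 3
- bleeding index: 3
- probing depth: 1

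This gives 25 per arm and 75 over three arms, before any comparison of diary days. The plan does not say which of these will be run.

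**What the tests do when the rinses are identical.** Inputs:
- 90 patients in 3 groups (Study Protocol). Equal allocation is assumed, giving 30 per arm.
- Two-sided 0.05 for every test (Statistical Analysis Plan).
- Changes are assumed normal with the same true mean in every arm. That mean, in SD units of the change, is not in the documents and is varied.

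For each simulated trial, a Wilcoxon signed rank test was run in each arm and a Kruskal-Wallis test was run on the changes across the arms.

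| Shared change (SD) | Within-arm test significant | Arms disagree on significance |
|---|---|---|
| 0.3 | about 34% | about 67% |
| 0.4 | about 54% | about 74% |
| 0.5 | about 73% | about 58% |
| 0.75 | about 97% | about 8% |
| 1.0 | over 99% | under 1% |

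Kruskal-Wallis rejected in about 5% of trials throughout, as it should.

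**Check on the last column.** If each arm is significant independently with probability p, the arms disagree with probability 1 − p³ − (1 − p)³. At p = 0.34 this is 1 − 0.039 − 0.287 = 0.67. At p = 0.54 it is 1 − 0.157 − 0.097 = 0.75. At p = 0.73 it is 1 − 0.389 − 0.020 = 0.59. At p = 0.97 it is 1 − 0.913 − 0.000 = 0.09. These agree with the simulation to about one percentage point. The maximum, 75%, occurs at p = 0.5.

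**Sensitivity to arm size.** With 24 per arm, the within-arm test is significant in about 28%, 45% and 63% of arms at 0.3, 0.4 and 0.5 SD. The arms disagree in about 61%, 74% and 70% of trials.

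**The case against.** The strongest reply is that no misuse is declared. The between-group test is named first, the predictor is a between-arm question, and no sentence says that within-arm results will support a claim about a rinse. This stands. A reader might infer from the shared threshold that the within-arm tests are meant as efficacy analyses, but the documents do not say so. They also do not rank the tests or limit how they may be read.

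Other stronger readings do not hold:

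- A reader might conclude that within-arm results say nothing about any rinse. That goes too far: a rinse effect may be part of the change, but it cannot be separated from the rest.
- A reader might expect a significant swelling test to be reported as a benefit. Swelling and mouth opening are defined against the preoperative value, so a significant pre-post result after surgery would ordinarily show worsening.
- A reader might take "having asymptomatic unilateral mandibular impacted third molars" to mean a pain-free baseline score. It describes the molars. With no preoperative diary value, within-arm pain tests could only compare postoperative days.
- A reader might assume that the arms will usually disagree on significance. That holds only for moderate shared changes. If surgery produces large changes, the arms nearly all agree.
- A reader might blame the lack of an unrinsed arm, or extend the point to equivalence with the control. A randomised comparison against an active rinse is valid, and equivalence is a separate matter that this text does not raise.

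Two further points stand. Whether second-molar periodontal status at 1 month differs from its preoperative value is a legitimate descriptive question; an estimate with a confidence interval answers it. Also, Kruskal-Wallis is an omnibus test and the plan names no pairwise follow-up. That gap needs its own attention, and within-arm tests do not fill it.

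**Conclusion.** The concern holds as a weakness in the choice and labelling of analyses. The planned within-arm tests do not address the stated predictor. Neither their significance nor its pattern across arms can be attributed to a rinse. The randomised comparison is planned and remains valid, so the trial's main inference is not invalidated. The risk is misreading, and the correction is cheap enough that it should be made.

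The size depends on a shared change that the documents do not give. Across 0.3 to 1 SD, identical rinses yield a significant within-arm test in about 34% to over 99% of arms. Disagreement between arms peaks at about 74% at 0.4 SD and falls below 1% at 1 SD. These figures assume equal arms of 30, normal changes and the same true change in each arm. That a within-arm test cannot separate rinse from recovery needs none of these assumptions.

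**What to change.** In the Statistical Analysis Plan:

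1. Replace the within-arm Wilcoxon tests with descriptive summaries: median change with a 95% confidence interval at each time point, without p-values. Where there is no preoperative value, as for the diary outcomes, summarise by postoperative day.
2. Apply the p < 0.05 rule only to the randomised between-arm comparisons.
3. For mouth opening, facial distances, plaque, bleeding and probing depth, state that the between-arm comparison is of change from the preoperative value.
4. State that conclusions about a rinse rest only on the between-arm comparisons.

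The cost is a change of wording and fewer significant p-values to report. No extra patients, visits or measurements are needed, and the within-arm course over time is still shown.
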